## 7.3 Analysis and Presentation of the Secondary Immunogenicity Endpoint

The secondary immunogenicity endpoint is seroconversion for anti-CTH522 IgG antibody at any time points after vaccinations.

All immunogenicity endpoints will be analysed using the FAS and the subjects will be evaluated according to the actual treatment received. The PP analysis set will be used as supportive.

[figure not shown]
### 7.3.1 Anti-CTH522 IgG Antibody

The anti-CTH522 IgG titre will be summarised by visit: Number of subjects with available titre, geometric mean, geometric coefficient of variation (CV), median, minimum, and maximum will be presented for actual values and ratio to baseline (fold difference).

Percentage of subjects achieving seroconversion for anti-CTH522 IgG at any time point after first vaccination will be presented for

- 4-fold increase compared to baseline
- 10-fold increase compared to baseline

The number and percentage of subjects achieving 4-fold increase respectively 10-fold increase seroconversion for anti-CTH522 IgG will be summarised by visit including cumulative numbers over

time. If a subject achieves seroconversion at a visit, the same subject will be counted as having seroconversion at all subsequent visits in the cumulative summary.

In addition to the descriptive presentation outlined above, the following analyses which are not described in the protocol will be presented:

The anti-CTH522 IgG titre will be compared by a non-parametric Mann-Whitney-Wilcoxon exact two-sample test for

- Cohort A-C vs Cohort D at Day 28
- Cohort A-C vs Cohort E at Day 28
- Cohort A vs Cohort B at Day 126
- Cohort A vs Cohort C at Day 126
- Cohort B vs Cohort C at Day 126
- Cohort A vs Cohort D at Day 126
- Cohort A vs Cohort E at Day 126

Using SAS® Proc NPAR1WAY with option *exact wilcoxon*.

If the value of anti-CTH522 IgG is below lower limit of quantification (LLOQ), then the value is set to LLOQ to be able to calculate the change.

The anti-CTH522 IgG titre will also be presented on a log scale in a spaghetti-plot by subject and day. The geometric mean will be presented in a plot by treatment group and day.

The cumulative proportion of subjects achieving 4-fold increase respectively 10-fold increase seroconversion for anti-CTH522 IgG will be presented in a plot by treatment group and day. In addition, a plot showing the median titre will be presented by treatment group and day.

All data will be listed.

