8.1 Overall trial design

The present trial is a phase I, double-blind, parallel, randomised, and placebo-controlled trial of the chlamydia vaccine, CTH522, in healthy adults. The trial will be conducted at Imperial College Healthcare NHS Trust (ICHT), London, in the UK.

[figure not shown]
It is planned to randomly assign 66 subjects into six cohorts. Cohorts A-D investigate CTH522-CAF01 administered IM in two doses (85 µg and 15 µg). Cohort E investigates CTH522-CAF09b administered IM in one dose (85 µg). Cohort F is the placebo group (Figure 1). The enrolled subjects will complete 12 trial visits (Vs) (Table 3).

All subjects in the active groups (cohort A-E) will receive three IM injections of the adjuvanted CTH522 and some (cohort B and C) will receive the non-adjuvanted CTH522 via the TO or ID route (given at the same time as the 2nd and 3rd IM vaccinations). All active groups will receive TO administration as a boost at Day 140 of either the non-adjuvanted CTH522 (12 µg in each eye) or placebo.

- Cohort A will receive three IM vaccination of 85 µg CTH522-CAF01. This cohort is divided into two groups: A1 will receive ID placebo at Day 28 + Day 112, and TO placebo at Day 140, while A2 will receive TO placebo at Day 28 + Day 112, and non-adjuvanted TO CTH522 boost at Day 140.
- Cohort B will receive three IM vaccinations of 85 µg CTH522-CAF01. This cohort is divided into two groups: B1 will receive TO vaccination of the non-adjuvanted CTH522 at Day 28 and 112 and TO placebo at Day 140, while B2 will receive the same for Day 28 and 112, but non-adjuvanted TO CTH522 boost at Day 140. The two additional TO doses of CTH522 (12 µg in each eye) are administered in each eye. The rationale for this schedule is to investigate the impact of simultaneous TO administration of the antigen on the immunogenicity results.
- Cohort C will receive three IM vaccinations of 85 µg CTH522-CAF01. This cohort is divided into two groups: C1 will receive ID vaccination of the non-adjuvanted 24 µg CTH522 at Day 28 and 112 and TO placebo at Day 140, while C2 will receive the same for Day 28 and 112, but TO 12 µg CTH522 boost in each eye at Day 140. The rationale for this schedule is to investigate the impact of simultaneous ID administration of the antigen on the immunogenicity results.
- Cohort D will receive three IM vaccinations of 15 µg CTH522-CAF01. The rationale for the A and D cohorts is to investigate the impact of the two IM CTH522 doses on the immunogenicity results.

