11.4.3 Exposure and treatment compliance

It is planned that 91% of the subjects will randomise to receive the 85 µg CTH522-CAF01, 15 µg CTH522-CAF01, or 85 µg CTH522-CAF09b in addition to the successive administration of the non-adjuvanted CTH522 or the placebo. The other 9% of the randomised subjects will receive only the placebo consisting of 0.9% NaCl. Treatment compliance is documented as a drug accountability log.

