### 3.2.1 Treatment labels

The cohort labels will be used as treatment labels in tables, figures, and listings as described in Table 2. Cohorts who had the same treatment at first, second and/or third vaccination will when relevant be grouped at timepoints where the treatments received were similar, and will be labelled accordingly:

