### 5 Planned Statistical Methods

If nothing else is stated, all tables, figures and listings will be presented by treatment group (i.e., A1, A2, B1, B2, ..., F2), and will be reported by actual received treatment for the SAF. A subject who receives more or less of the treatment than intended, will be presented in the cohort they belong to. If any subjects receive incorrect treatment, they will be presented separately.

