#### 5.1 Statistical Considerations

Baseline is defined as the last assessment with available data prior to the first administration of trial medication. Day 0 is the day of first administration with IMP. Assessments from scheduled visits will be presented when available, otherwise the first unscheduled visit succeeding the scheduled visit in question is used.

Categorical data will be summarized by treatment group, using number and percentages of subjects. For calculation of percentages the denominator will either be the number of subjects in the analysis set or the number of subjects in the analysis set with non-missing values. Continuous data will be presented using the number of subjects (n), mean, standard deviation (SD), median, minimum, and maximum if nothing else is stated. Both the absolute values and the change from baseline will be presented.

Descriptive statistics for all endpoints will be presented by treatment group and visit (if applicable) using observed cases, i.e., no imputation of missing data will be performed.

All statistical tests will be two-sided and performed on a 5 % significance level. Estimated treatment differences and 95 % confidence intervals (CI) will be presented together with the corresponding p-value.

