## 8 Deviations from Protocol

- The periods where the events for three of the co-primary endpoints (solicited local injection site reactions, solicited ocular reactions, and solicited systemic reactions) are considered were not specified in the protocol but in the subjects' diary. In this SAP the vaccination days are detailed as well as the 14-day period after vaccinations.
- For the co-primary endpoint *Solicited systemic reactions after IM and/or ID administration*, the PT *Pyrexia* should be used for temperatures above 38.3°C only, which is not as in the FDA guidelines presented in the protocol Appendix 1. Appendix 1 is stating temperatures above 38.0°C. For increased temperatures at or below 38.3°C, the PT *Body temperature increased* is used and thus not included as events. If the temperature is unknown, *Pyrexia* will be used, and the event included.
- The Wilcoxon tests of anti-CTH522 IgG titre are not described in the protocol.
- Presentations and analyses are adapted to fit the nature of the data.

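### Must SAP 7.3.1 name the estimate and confidence interval that go with the seven exact Wilcoxon comparisons of IgG titre?

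*SAP*

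**What the plan says.** SAP 5.1 sets two-sided testing at 5% and then a general reporting rule: "Estimated treatment differences and 95 % confidence intervals (CI) will be presented together with the corresponding p-value". It makes no exception for rank tests.

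SAP 7.3.1 plans titre summaries by visit: number of subjects, geometric mean, geometric CV, median and range, for actual values and for the ratio to baseline. It then adds the tests: "The anti-CTH522 IgG titre will be compared by a non-parametric Mann-Whitney-Wilcoxon exact two-sample test for" seven contrasts. These are A-C against D and A-C against E at Day 28, and A against B, A against C, B against C, A against D and A against E at Day 126. The only software option named is the exact Wilcoxon. For low values: "If the value of anti-CTH522 IgG is below lower limit of quantification (LLOQ), then the value is set to LLOQ".

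On grouping, SAP 5 gives the default, where nothing else is stated: "all tables, figures and listings will be presented by treatment group (i.e., A1, A2, B1, B2, ..., F2"). SAP 3.2.1 adds that cohorts with the same treatment "will when relevant be grouped at timepoints where the treatments received were similar".

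SAP 8 records: "The Wilcoxon tests of anti-CTH522 IgG titre are not described in the protocol". SAP 7.7 asks that these tests be interpreted with care. Protocol 11.4.5 plans only a descriptive presentation of seroconversion.

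**The concern.** Read together, 5.1 owes the reader an estimate and interval for each contrast, and 7.3.1 does not define them. A Hodges-Lehmann shift on raw titre, the same shift on log titre, a ratio of geometric means and a ratio of fold rises would all satisfy 5.1. The choice could therefore be made after unblinding.

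The contrasts matter for interpretation. On dose, for example, Protocol 8.1 says: "The rationale for the A and D cohorts is to investigate the impact of the two IM CTH522 doses on the immunogenicity results". With small cohorts, a non-significant rank test cannot separate a similar response from too few subjects, and a highly significant one does not show how large the difference is.

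The default tables also do not show every pooled cohort that is tested. A reader could meet a p-value for Cohort A against Cohort D at Day 126 with geometric means shown only for A1, A2, D1 and D2.

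**Working it through.** **1. Which tested groups lack a label.** SAP Table 2 against the seven contrasts:

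| Contrast | Day | Label in Table 2 |
|---|---|---|
| A-C v D | 28 | both sides (Day 0 block) |
| A-C v E | 28 | both sides (Day 0 block) |
| B v C | 126 | both sides |
| A v B | 126 | B only |
| A v C | 126 | C only |
| A v D | 126 | neither |
| A v E | 126 | neither |

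The Day 28 rows use the Day 0 labels because Protocol 8.2 draws the Day 28 blood before the second vaccination. The gap is therefore limited to pooled A, D and E at Day 126. Up to that day the two halves of each of these cohorts differ only in whether the placebo was given ID or TO, so the grouping sentence in 3.2.1 can reasonably cover them.

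**2. Whether the pooled figures can be recovered.** The planned tables give n and the geometric mean (GM) for each half, so

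GM(A) = exp{[n1·ln GM(A1) + n2·ln GM(A2)] / (n1 + n2)},

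and likewise for D and E. Under the usual definition of geometric CV, the log-scale SD is √ln(1 + CV²), which leads to an approximate interval for a ratio. All data are also listed.

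**3. Cohort sizes.** Protocol 11.4.3 states: "The other 9% of the randomised subjects will receive only the placebo consisting of 0.9% NaCl". So 0.09 × 66 = 5.94, about 6 placebo, and 0.91 × 66 = 60.06, about 60 active. An equal split over five cohorts gives 60/5 = 12. The split is an assumption, because the sizes stand in a figure that is not available. Day 28 is then 36 against 12. The documents give no SD, effect size or power figure to reproduce.

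**4. What the p-value carries.** Ranks do not change under a log transform, so the p-value is the same on raw and log titre. At 12 against 12 with complete separation, p = 2/C(24,12) = 7.4 × 10⁻⁷, whether the fold difference is 5, 50 or 500. In one constructed data set the Hodges-Lehmann ratios (95% CI) were 5 (3.4 to 7.3), 50 (34 to 73) and 500 (341 to 732). An estimate is informative, then, and 5.1 already requires one.

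**5. Chance of a non-significant result.** Assume a true 2-fold difference, 12 against 12 and a log10 SD of 0.3, 0.4 or 0.5. Simulated power is 0.616, 0.377 and 0.267, so 38%, 62% and 73% of trials are non-significant. Naming an estimator does not change these figures.

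**6. How much the choice of estimator moves the answer.**
- *Point estimate* (36 against 12, SD 0.4, true ratio 2.51). With 22% of the lower group at the LLOQ, the Hodges-Lehmann ratio is 2.32 and the geometric mean ratio 2.28: 2.32/2.28 = 1.02. With 50% at the LLOQ they are 1.79 and 1.87: 1.87/1.79 = 1.04.
- *Interval* (12 against 12, SD 0.4). Hodges-Lehmann about x/÷2.25, geometric mean ratio about x/÷2.20: 2.25/2.20 = 1.02.
- *Baseline adjustment.* The factor 2.20 at zero correlation with Day 0 becomes 2.12 at 0.3 and 1.98 at 0.5. The gain is near nil if most Day 0 values are at the LLOQ.

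**7. Whether one choice is clearly best.** The Hodges-Lehmann interval inverts the same test. Its limits are the 38th and 107th of 144 pairwise differences at 12 against 12 (coverage 95.5%), and the 134th and 299th of 432 at 36 against 12 (95.1%). That coverage holds only under a pure shift. At 36 against 12 with SD 0.3 against 0.5, simulated coverage falls to about 91 to 92%. With 50% of the lower group at the LLOQ, coverage of the true ratio is about 78 to 82%.

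**The case for a change.** The strongest case for a change is that it costs one sentence and makes the sponsor's own rule in 5.1 executable. The scale is a real choice: a shift on raw titre is a difference in titre units, and on log titre it is a ratio. The dose, route and adjuvant questions deserve an effect size fixed in advance, and hand-derived ratios are not pre-specified results.

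Much of this stands as description. The text is under-specified, the exact p-value does not show magnitude, and pooled A, D and E have no label at Day 126.

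It does not amount to a fault in the analysis. A late choice of estimator cannot alter significance, because the test, the contrasts and the days are fixed. The summaries in 7.3.1 are mainly geometric means, fold differences and log-scale plots, which lead an analyst to a ratio. On that scale the plausible candidates nearly agree (step 6). A baseline-adjusted model would add little, and the lack of Day 0 adjustment is not a defect in a randomised comparison.

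**Conclusion.** No change follows. This is a gap that analysts fill sensibly: 5.1 makes an estimate and 95% CI due, the summaries in 7.3.1 point to a titre ratio, and 3.2.1 allows the grouping that pooled A, D and E need at Day 126.

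The size is small. Between the two natural ratio estimators, the point estimate moved by about 2 to 4% and the interval factor by about 2% in the settings checked. These figures rest on an assumed 12 subjects per active cohort, an assumed log10 SD of 0.4 and roughly log-normal titres. Skewed data could separate the estimators further. The reading of the text does not depend on those assumptions.

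Fixing the Hodges-Lehmann interval in advance would not settle everything either, since it under-covers with unequal spread or many values at the LLOQ. The tests are declared additions that the SAP asks to be read with care, and no decision rule uses them. The primary safety analysis and the descriptive seroconversion endpoint are untouched.

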8.2 Trial procedures

At V1 (Day -90 to -1), the volunteers' eligibility is assessed according to the pre-specified inclusion/exclusion criteria and the informed consent is obtained. The medical history, vital signs (including BMI) are taken, physical and eye examinations are performed. Refer to Table 3 for eye examination method required at V1. Concomitant medications (CM) and AEs are recorded. Blood samples for screening of hepatitis B and C, HIV, syphilis and safety biochemistry/haematology are drawn. Urine is collected for pregnancy test and PCR for *C. Trachoma* and gonorrhoea infections.

At V2 (Day 0), the inclusion/exclusion criteria are assessed again. Eye and symptom-direct physical examination are performed and vital signs are taken. Refer to Table 3 for eye examination method required at V2. Any AEs and CMs are reviewed and recorded. Urine is collected for pregnancy test. The volunteers are randomised according to the randomisation scheme via the eCRF. Before the 1st IM vaccination, blood samples for safety and immunogenicity determination (please refer to type of tests in Table 4) are drawn and ocular samples are taken. The volunteers (hereafter subjects) receive the 1st IM vaccination. The subjects are observed for any immediate AE for 60 minutes after the vaccination. The diary card is issued with instructions before discharge from the site.

At V3 (Day 14), the diary card is collected and reviewed. Adverse events and CM are reviewed and recorded. Vital signs are taken and symptom-directed physical examination is performed as necessary. Blood samples for safety and immunogenicity (please refer to type of tests in Table 4) are drawn.

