8.3.2 Exclusion criteria

General

- EX1: Is positive for *C. trachomatis* via urine PCR or has a known history of *C. trachomatis*
- EX2: Is positive for gonorrhoea via urine PCR test, or HIV, hepatitis B/C, syphilis via blood tests
- EX3: Has a significant active disease such as cardiac, liver, immunological, neurological, psychiatric or clinically significant abnormality of haematological or biochemical parameters
- EX4: Has BMI $\geq 35 \text{ kg/m}^2$
- EX5: Is currently participating in another clinical trial with an investigational or non-investigational drug or device, or was treated with an investigational drug within 28 days before the first vaccination
- EX6: Has received, or plans to receive, any immunisation within 14 days of the start of the trial or during the trial immunisations
- EX7: Is currently receiving treatment with systemic immunosuppressive agents. Topical steroids are allowed unless applied to the IM or ID injection site
- EX8: Has a condition which in the opinion of the investigator is not suitable for participation in the trial
- EX9: Is known or confirmed to have allergy to any of the vaccine constituents

- EX10: Is unable to refrain from use of contact lenses. Contact lenses should be avoided two days before TO administration and for seven days later (longer if any ongoing local eye AE)
- EX11: Has any evident ocular disease upon eye examination (prior to first vaccination) or any medical history of ocular disease that, in the opinion of the investigator, may impact the subject's participation in the trial

Female-specific

- EX12: Is pregnant (positive pregnancy test) or breastfeeding or not willing to use contraception during the trial
- EX13: Has confirmed history of pelvic inflammatory disease or significant gynaecological diseases

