12.1 Risks and benefits

At present, there is only data available for CTH522 with or without the adjuvants CAF01 or Al(OH)₃ from a completed clinical trial that included 35 adult female volunteers [9]. From this trial, safety data where CTH522-CAF01 have been administered IM are known. The related AEs (> one in ten subjects) after IM administration of CTH522-CAF01 reported were:

- injection site pain, injection site tenderness and injection site movement impairment after IM vaccination
- sneezing, nasal congestion and rhinorrhoea after intranasal vaccination
- systemic reactions after IM or IN vaccination were headache, fatigue, malaise and myalgia

The most frequently reported treatment-emergent AEs were headache, oropharyngeal pain, and dysmenorrhoea. Please refer to the IB for more information.

Based on general considerations, experience from clinical trials with CAF01, CAF09b and CTH522, the IMPs to be used in the present trial are expected to be safe.

Anaphylactic reactions are very rare. However, appropriate medical treatment and trained staff will be available in case an anaphylactic reaction occurs.

Vasovagal syncope (i.e. fainting), may occur. It will be attempted to minimise the occurrence of this reaction, by allowing the subjects to lie down during the administration of vaccine and blood drawings.

The trial personnel performing the procedures will inform the subjects on the procedures before blood drawings and administration of vaccine, and it will be emphasised to the subject, that participation is voluntary and that he/she at any time can withdraw from the trial.

This is a healthy volunteer trial, so there will be no direct health benefit to the individual subject. However, they will undergo general health and sexually transmitted infection screening. Sexually transmitted infection may be asymptomatic, and if diagnosed, the subjects will be counselled and offered referral to the confidential service provided by their local NHS genitourinary medicine clinic. If trial results are satisfactory, further clinical trials will be initiated and may lead to a marketed vaccine against trachoma and/or genital chlamydia.

The subjects will receive payment to compensate them for their time, inconvenience, travel expenses, etc. They will be paid £100 per scheduled clinic visit, to a maximum of £1200, paid as a lump sum at the end of participation. Volunteers who attend screening but who are not enrolled will not receive payment.

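### The seven IgG comparisons leave out the Day 0 titre and name no effect estimate, although SAP 5.1 promises one; a baseline-adjusted geometric mean ratio should stand beside the exact Wilcoxon tests

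*SAP*

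**What the plan says.** SAP 7.3.1 states that "The anti-CTH522 IgG titre will be compared by a non-parametric Mann-Whitney-Wilcoxon exact two-sample test for" cohorts A–C v D and A–C v E at Day 28, and A v B, A v C, B v C, A v D and A v E at Day 126. The call is SAS NPAR1WAY "with option *exact wilcoxon". No covariate, stratum or change score is named for the tests.

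SAP 5.1 sets the general rule: "All statistical tests will be two-sided and performed on a 5 % significance level". Its next sentence commits to showing estimated treatment differences and 95% confidence intervals together with the p-value. SAP 7.3.1 names neither for these seven tests.

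A baseline titre exists. SAP 5.1: "Baseline is defined as the last assessment with available data prior to the first administration of trial medication". Protocol 8.2, for V2 (Day 0): "Before the 1st IM vaccination, blood samples for safety and immunogenicity determination" are drawn, and Protocol Tables 3 and 4 mark serum IgG ELISA at that visit. SAP 7.3.1 uses this value twice: titre summaries "will be presented for actual values and ratio to baseline (fold difference", and seroconversion counted at 4-fold and 10-fold over baseline. Titres below LLOQ are set to LLOQ.

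SAP 8 records that the Wilcoxon tests are not in the protocol. SAP 7.7 leaves them unadjusted for multiplicity and asks for cautious interpretation.

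**The concern.** These seven contrasts are the only between-group tests that bear on the secondary IgG objectives of dose, route and adjuvant. As specified, each yields a p-value and no measure of how far apart the groups are. In a small phase I trial the size of the difference and its uncertainty are what a later dose or adjuvant decision would draw on.

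The tests also leave aside a pre-vaccination measurement of the same variable. If baseline titre varies between subjects and predicts the later titre, adjusting for it narrows the interval. Baseline variation is possible. Exclusion criterion EX1 covers anyone positive for C. trachomatis "via urine PCR or has a known history of" infection, but no entry serology is listed for C. trachomatis, and Protocol 12.1 notes "Sexually transmitted infection may be asymptomatic". Adults with unrecognised past infection, and some antibody, could therefore enter.

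**Working it through.** **No planned figure to reproduce.** Protocol 11.4.8 and SAP 3.3 say that no sample size calculation was made. The documents give no SD, effect size, LLOQ value, baseline distribution or baseline/post-vaccination correlation (ρ). Everything below that needs one of these rests on an assumption.

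**Where baseline and estimates appear in SAP 7.3.1**

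| Analysis | Uses Day 0 titre | Estimate and interval for the group difference |
|---|---|---|
| Titre summary by visit | Yes, as a ratio | No (descriptive) |
| 4-fold and 10-fold seroconversion | Yes | No (descriptive) |
| Seven exact Wilcoxon tests | No | None named |

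**Group sizes (assumed).** They are in Figure 1, which is not shown. Protocol 11.4.3 gives 9% placebo: 6/66 = 9.1%, leaving 60 active subjects. Five equal active cohorts give 60/5 = 12. Day 126 contrasts are then 12 v 12 and Day 28 contrasts 36 v 12.

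**Variance reduction without an LLOQ floor.** With ANCOVA on log titre the residual variance is (1 − ρ²) times the unadjusted variance, and the interval shortens by 1 − √(1 − ρ²).

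- ρ = 0: reduction 0%.
- ρ = 0.3: 0.3² = 9%; interval 5% shorter.
- ρ = 0.5: 0.5² = 25%; interval 13% shorter.
- ρ = 0.7: 0.7² = 49%; interval 29% shorter.

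**With baselines floored at LLOQ.** Ties at LLOQ weaken the correlation that can be used. Variance reduction, as the square of the correlation after flooring:

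| Share of baselines at LLOQ | Latent ρ 0.3 | 0.5 | 0.7 |
|---|---|---|---|
| 50% | 6.6% | 18.5% | 36.0% |
| 80% | 3.8% | 10.8% | 21.0% |
| 95% | 1.5% | 4.1% | 8.1% |
| 100% | 0 | 0 | 0 |

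**Cost of estimating the slope.** These are large-sample figures. At 12 v 12 the error degrees of freedom before the covariate are 22, and the usual correction for a normal covariate multiplies the variance by 1 + 1/(22 − 2) = 1.05. The net ratio at ρ = 0.5 without a floor is 0.75 × 1.05 = 0.79. With 80% at LLOQ it is (1 − 0.108) × 1.05 = 0.94. With 95% at LLOQ it is (1 − 0.041) × 1.05 = 1.01, that is, no gain. Without a floor, break-even is where 1 − ρ² = 1/1.05, so ρ is about 0.22.

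**Simulated power** (12 v 12, normal log titres, true difference 1 SD, two-sided 5%):

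| Setting | Exact Wilcoxon | ANCOVA |
|---|---|---|
| ρ = 0, no floor | 60% | 62% |
| ρ = 0.5, no floor | 61% | 75% |
| ρ = 0.5, 80% at LLOQ | 60% | 68% |
| ρ = 0.5, 95% at LLOQ | 62% | 66% |

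In the floored settings an unadjusted t-test on the same data reaches 64–66%. Of the 8 points gained with 80% at LLOQ, at least half comes from the normal model applied to normal data. With 95% at LLOQ essentially all of it does. ANCOVA's type I error stayed between 3.8% and 5.6% in the settings run.

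**Chance imbalance.** At 12 v 12 the baseline difference has SD √(2/12) = 0.41 of the baseline SD. A gap above 0.5 SD therefore arises in 2 × [1 − Φ(0.5/0.41)], about 22%, of contrasts. On average it passes to the outcome as ρ × gap: at ρ = 0.5, 0.5 × 0.5 = 0.25 SD.

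**Fold-rise as the tested variable.** Its variance ratio is 2(1 − ρ) with equal SDs, which exceeds 1 when ρ is below 0.5. At ρ = 0, no floor and a difference of 1.2 SD, Wilcoxon power falls from 77% on the raw titre to 48% on fold-rise.

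**The case against.** The best defence is that baseline may carry almost no information. EX1 removes urine-PCR positives and known past cases, and the LLOQ rule turns every baseline below LLOQ into one constant. If a few subjects with unrecognised past infection are the only ones above it, the ANCOVA slope rests on one or two high-leverage points per contrast. This stands as a limit on the expected gain. It does not show that baselines are flat: the documents give no share at LLOQ, and the previous trial's absence of seroconversion in placebo subjects concerns change and not level.

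Second, the exact Wilcoxon test needs no distributional model in small groups, and ANCOVA does. This also stands. With heavy-tailed data (t, 4 df) and ρ = 0, ANCOVA had 66% power against 72% for Wilcoxon. It is a reason to keep the exact test.

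Third, baseline already enters the secondary endpoint, seroconversion, and the ratio summaries, and individual plots and listings would reveal an imbalance. True, but none of these gives an adjusted group difference.

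Fourth, the tests are SAP additions with a caution attached. That lowers the stakes; it does not supply the missing interval. A Hodges–Lehmann shift on the log scale would supply one without baseline, but would leave the Day 0 titre unused.

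A reader might infer that the planned tests are biased, that precision is certainly being lost, or that ANCOVA should replace the Wilcoxon test. The documents support none of these. Randomisation makes the unadjusted comparison valid, the correlation is unknown, and replacing the exact test would trade robustness for a gain that may be nil.

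**Conclusion.** Two things hold on the documents alone: the Day 0 titre is left out of the seven tests, and no estimate or interval is named for them despite the commitment in SAP 5.1. The size of the precision loss does not follow from the documents. Before the slope cost of about 5% at 12 v 12, it runs from nil to about half the variance (49% at ρ = 0.7 without a floor), and it is small if most baselines are at LLOQ. The correlations, the LLOQ shares, normality on the log scale and 12 per cohort are all assumptions; the variance reductions before the slope cost do not depend on cohort size. This is a matter of precision and reporting in supportive analyses, and it leaves the validity of the planned tests untouched. The firmer ground for acting is the missing effect estimate; use of baseline is a sensible addition to it.

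**What to change.** In SAP 7.3.1, before unblinding:

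- Keep the seven exact Wilcoxon tests as written.
- Add, for the same contrasts and visits, an ANCOVA on log10 titre with treatment group and log10 baseline titre. Report the back-transformed adjusted geometric mean ratio with its 95% CI. This gives the difference and interval that SAP 5.1 calls for, on the scale of the geometric means already planned.
- Report the number of baselines at LLOQ by cohort. If many are at LLOQ, add rank ANCOVA as a check. If all baselines in a contrast are equal, drop the covariate and report the unadjusted ratio.
- Do not substitute a test on fold-rise.
- List the added analysis in SAP 8, as is done for the Wilcoxon tests.

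The cost is SAP wording and a short program, with no new sampling. The statistical price is one degree of freedom, about 5% of variance at 12 v 12 if baseline proves uninformative, and a model assumption that keeping the exact test contains.
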